6.4. Consent

Patients will be provided the Informed Consent Form and this will be reviewed by the Study Personnel. Patients will be encouraged to take the form home and review with their family if possible

6.5 Baseline period, Week 0

Once a patient has signed the ICF, a 12 lead ECG will be obtained. The long term cardiac monitor will be placed at the end of HD3 prior to Week 0 and removed at the beginning of HD3 of Week 0. Weight, pulse, and blood pressure will be recorded. Medical history and demographic data will be collected. Medications will be recorded. The hemodialysis prescription for target weight and dialysate potassium and calcium will be recorded.

Before each hemodialysis session in Week 0, blood samples will be collected and sent to the clinical laboratory. The Renal Function Panel and magnesium levels will be determined with these samples before the first dialysis session of the week (HD1). Serum pregnancy test will be measured for females of child-bearing potential.

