6.6 Randomization

Randomization will occur at any time in Week 0 prior to HD3. This will be done using the REDCap system and will assign patients 1:1 to either continue usual care or to receive patiromer as detailed below.

6.7 Open-label patiromer and dose titration, Weeks 1, Week 2, Week 3, Week 4.

Patients randomized to the patiromer arm will initiate on 8.4 g/day (one pack) given once a day with breakfast or lunch, to start after HD3 at the end of Week 0. The patient is instructed to not take any other medications for three hours before or three hours after patiromer.

The patiromer dose will be titrated based on serum potassium concentrations on HD1 of weeks 1, 2, and 3. Patiromer will be increased by 8.4 g/day if $K \geq 5.5$ meq/L, decreased by 8.4 g/day if $K < 4.5$ mEq/L, and patiromer will be discontinued if $K < 4$ mEq/L.

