6.10 Seven day cardiac monitor

The long-term heart monitor (LTHM) to be used in this study is a dual –channel wearable cardiac monitor that is applied as a skin patch. The Medicomp Telepath records cardiac rhythms for up to 7 days (medicompinc.com; last accessed 5/1/19).

The first LTHM, Telepatch #1 will be applied at the end of HD3 prior to Week 0 and removed at the beginning of HD3 of Week 0. The second LTHM, Telepatch #2, will be applied at the end of HD3 at the end of HD3 and removed at the beginning of HD3 of Week 4.

When the cardiac monitor is applied to a patient, a user guide and a symptom diary will be provided.

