6.12 Concomitant medications

Except for those listed in the exclusion criteria, all medications (prescription or over-the-counter) initiated prior to enrollment may be continued during the course of the study.

All medications that are continued from the start of the study or that are started during the study (other than the study medication) including prescription or over-the-counter will be documented by the study team.

6.13 Follow-up evaluations Weeks 1, 2

A member of the study team will see the patient at the start of HD1 Week 1. Weight, pulse and blood pressure will be recorded. A pre-dialysis serum potassium lab sample will be collected and sent to the clinical lab. Concomitant medications will be recorded.

With study team visit on HD2 or HD3 of Week 1, the patiromer dose will be titrated based on the pre-dialysis potassium measured at HD1. Patiromer will be increased by 8.4 g/day if $K \geq 5.5$ meq/L, decreased by 8.4 g/day if $K < 4.5$ mEq/L, and patiromer will be discontinued if $K < 4$ mEq/L.

6.14 The assessment period Weeks 3, 4 and 6

A member of the study team will see the patient at the start of HD1 Week 3 and HD1 Week 4. Weight, pulse and blood pressure will be recorded. A pre-dialysis serum potassium lab sample will be collected and sent to the clinical lab to measure potassium. Concomitant medications will be recorded.

With study team visit on HD1 of Week 3, the patiromer dose will be titrated based on the pre-dialysis potassium measured at HD1. Patiromer will be increased by 8.4 g/day if $K \geq 5.5$ meq/L, decreased by 8.4 g/day if $K < 4.5$ mEq/L, and patiromer will be discontinued if $K < 4$ mEq/L.

The long term heart monitor (LTHM; Telepatch #2) will be placed at the end of HD3 Week 3 and removed at the beginning of HD3 of Week 4.

With study team visit on HD1 of Week 6, weight, pulse and blood pressure will be recorded. A pre-dialysis blood sample will be collected and sent to the clinical lab for a renal function panel. Concomitant medications will be recorded.

6.15. Withdrawal of subjects.

A subject may discontinue participation in the study at any time without being obligated to give a reason, although they are free to do so if they wish.

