8.2 Secondary endpoints

Because study sample size is limited and is based only on the amount of information needed to adequately assess the primary hypothesis, this pilot study will have limited power to effects on secondary endpoints. We consider these measurements to be exploratory. A significant effect on the exploratory endpoints will be considered in light of the results of the primary analysis.

Differences in laboratory values between the treatment groups will be determined by analysis of variance (ANOVA). The long-term heart monitor results will be compared in the following ways:

Group 1: Individual patient compared by their LTHM #1 vs LTHM #2;

Group 2: Individual patient compared by their LTHM #1 vs LTHM #2

Group 1 LTHM #1 vs Group 2, LTHM #1;

Group 1 LTHM #2 vs Group 2, LTHM #2

Each monitor will be assigned a point score, counting only the most severe event.

Finding	Score
Sustained VT, VF and/or asystolic cardiac arrest (CPR required)	10
Nonsustained VT (\geq 3 beats but $<$ 30 seconds) and/or $>$ 5 second pause during daytime (0800-2000) and/or atrial fibrillation ($>$ 30 seconds)	3
PVC $>$ 1000/24h and/or $>$ 3 second pause during daytime (0800-2000)	2
PVC $>$ 500/24h and/or or HR $<$ 40 for 5 consecutive beats during daytime (0800-2000)	1

Monitor period scores will be tabulated, and differences in period scores addressed by ANOVA.

Heart rate variability will be recorded in time-domains from the LTHM and periods will be compared.

The QT intervals will be compared for the LTHM periods in two different procedures. The mean QTc will be determined for each 7 day period, and groups will be compared. In addition, in the LTHM will collect 30 second rhythm strips in the last dialysis session (HD3) of week 4, and QTc will be determined and compared between the treatment groups.

Bradyarrhythmias will be recorded and classified for comparison as follows: asystole > 5 seconds with syncope, third degree AV block, second degree AV block, sinus pause > 3 seconds, and sinus bradycardia < 40 bpm.

9. Monitoring

The sponsor of the study, Relypsa, will provide study monitoring at a mutually agreeable time, during normal business hours.

10.. Schedule of Assessments

Procedures/Visits	Pre- Week 0	Week 0			Week 1			Week 2			Week 3			Week 4		
		Visit	HD1	HD2	HD3	HD1	HD2									
Week		1		2		3		4		5						
Determination of Elevated K Episodes	X															
Informed Consent	X															
Medical History and Demography		X														

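### The in-dialysis QTc strips are planned for HD3 of Week 4, but the patch comes off as that session begins; the strips also have no Week 0 counterpart

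*Combined protocol and SAP*

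**What the plan says.** Section 8.2 gives two QTc procedures for the long-term heart monitor (LTHM). The first is a summary over the whole wear period: "The mean QTc will be determined for each 7 day period, and groups will be compared". The second is specific to dialysis: "the LTHM will collect 30 second rhythm strips in the last dialysis session (HD3) of week 4", with QTc from those strips compared between arms. No strips are named for Week 0.

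The wear window is set elsewhere. Section 6.14 says the second patch "will be placed at the end of HD3 Week 3 and removed at the beginning of HD3 of Week 4", and section 6.10 likewise has it "removed at the beginning of HD3 of Week 4". For the first patch, section 6.5 says "The long term cardiac monitor will be placed at the end of HD3 prior to Week 0 and removed at the beginning of HD3"; the session meant there is the Week 0 one. Section 6.10 states that the device "records cardiac rhythms for up to 7 days".

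Section 8.2 also lists four monitor comparisons: first against second monitor within each group, and group against group on each monitor separately. It does not describe a between-group comparison on the second monitor that uses the first-monitor value.

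**The concern.** The strips must come from the patch, and the patch is not on the patient for the session in which they are to be taken. Nothing else fills the gap. The only 12-lead ECG is in Week 0 at an outpatient cardiology clinic (6.11). The 48-hour monitor description in 6.2 has its last window ending at HD3 as well.

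The background in 3.1 gives the dialysis session particular weight: it places the steep potassium fall in the first hour and cites a study in which 70.0% of captured arrhythmia events occurred during the session. A strip taken as the session starts misses most of that fall.

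Without usable strips, QTc rests on the whole-period mean. That mean would show a sustained difference between arms but would dilute one limited to dialysis. The documents do not establish that a dialysis-limited pattern exists. What is at stake is one exploratory comparison, plus the stated aim in 8.1 of trying out procedures for a larger trial.

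**Working it through.** **Plan's own figure.** The plan gives no precision or power figure for QTc. Its one design figure is 86% power for the primary endpoint (20 per group, difference 2, SD 2, two-sided 0.05). A two-sample t-test gives 86.9%, which agrees. Nothing below depends on it except the 20 per arm.

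**Inputs.**
- Session length 3 to 4 h: inferred from 3.1, which describes a first hour followed by a further 2 to 3 h.
- Recorder capacity: 7 × 24 = 168 h (6.10).
- Patch on at the end of one HD3 and off at the start of the next (6.5, 6.10, 6.14).
- Usual thrice-weekly spacing (assumption): counting from application at hour 0, the next three sessions end at hours 72, 120 and 168.
- Minutes of HD3 recorded before removal: not stated. Zero is the literal reading; 5 to 15 is assumed as a generous range.

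**Timeline against recording.**

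| Session | Hours from application | Within planned wear? | Capacity left at session end |
|---|---|---|---|
| HD1 | 68 or 69 to 72 | yes | 168 − 72 = 96 h |
| HD2 | 116 or 117 to 120 | yes | 168 − 120 = 48 h |
| HD3 | 164 or 165 to 168 | only its first minutes, if any | 168 − 168 = 0 h |

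The table applies to both patches, because both have the same wear window.

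**Part of HD3 from which strips could be drawn.** Minutes recorded divided by session length: 0% at literal removal; 5/240 = 2.1% at the low end of the assumed range; 15/180 = 8.3% at the high end.

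**Dialysis share of the whole-period mean.** Two sessions (HD1 and HD2) fall inside each recording: 2 × 3 = 6 h of 165 h = 3.6%, or 2 × 4 = 8 h of 164 h = 4.9%. In a time-weighted mean, a QTc difference confined to sessions would appear at between 6/165 and 8/164 of its size.

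**Is Week 0 a clean baseline?** Patiromer is "to start after HD3 at the end of Week 0" (6.7), so HD1 and HD2 of Week 0 both precede the first dose.

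**Precision with and without the first-monitor value.** In units of the between-patient SD of QTc, with n = 20 per arm:
- Unadjusted half-width of the 95% CI: t(0.975, 38) × √(2/20) = 0.640 SD.
- Adjusted: t(0.975, 37) × √(2/20) × √(1 − r²), where r is the correlation between the two monitor values.
- Equivalent sample size per arm: 20/(1 − r²).

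| r (assumed) | Half-width (SD) | Equivalent n per arm |
|---|---|---|
| 0.3 | 0.611 | 22.0 |
| 0.5 | 0.555 | 26.7 |
| 0.7 | 0.458 | 39.2 |

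The documents give no correlation, so this is a range and not an estimate.

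**The case against.** The wording conflict itself is not in doubt; the case against concerns its weight.

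- **An early strip may be all that was meant.** Section 8.2 gives no clock time, and a strip needs only 30 seconds. If the patch comes off just after the session starts, an early strip exists in both arms and can be compared. This is fair, but the result is then essentially a pre-dialysis QTc, and 8.2 should say so. Under literal removal there is no in-session strip at all.
- **Missing Week 0 strips do not invalidate anything.** This stands. A comparison of randomized arms at Week 4 is valid without a baseline; the loss is precision only.
- **Covariate adjustment is a separate improvement.** This also stands. The half-widths do not measure the timing conflict. They rest on assumed correlations and on two usable recordings from all 20 per arm, which is a best case because withdrawn patients are not replaced (6.16).
- **Section 6.2 describes 48-hour monitors.** If that were operative, full recordings of HD1 and HD2 would not be assured. However, 6.5, 6.10, 6.14 and the seven-day wording in 8.2 all describe the longer patch, so that is the better reading.
- **HD1 is not HD3.** HD1 follows the long gap and HD3 a short one. HD2 is the closer match if the short gap matters.
- **Stakes are low.** QTc is not named in any listed objective, and 8.2 calls these measurements exploratory. This limits the point to a minor one.

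**Conclusion.** The point holds. As written, the plan's only dialysis-specific QTc comparison cannot be carried out beyond, at best, the first minutes of the session: 0% of HD3 on the literal reading, 2% to 8% if removal is 5 to 15 minutes late (assumed) in a session of 3 to 4 h (inferred from 3.1). The strips have no Week 0 counterpart, which costs precision but not validity. The remaining QTc summary is 95% or more interdialytic.

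No sample size, primary analysis or decision is affected. It is a minor correction, worth making because the recordings needed for a workable version are already planned.

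**What to change.** **Main change, in 8.2.** Take the 30-second strips in HD1 of both Week 0 and Week 4, at the same fixed times after session start. Use HD2 of both weeks instead if a session after the short gap is wanted, as at HD3. Compare arms on the second-monitor QTc with the patient's own first-monitor value as covariate, alongside the within-group comparisons already listed.

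**Alternative.** Keep HD3 of Week 4 and remove the patch at its end, changing 6.10 and 6.14. This uses all 168 h of a seven-day recorder and leaves no margin for a late or long session, so it should be adopted only if capacity beyond 168 h is confirmed. Week 0 strips in HD3 would need the same change in 6.5.

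**Alongside.** Align the 48-hour wording in 6.2 with the seven-day patch, since the main change relies on the longer recording. Optionally, report mean QTc over the recorded HD1 and HD2 sessions on both monitors.

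**Cost.** No new device or visit is needed. Section 6.14 already provides that "A member of the study team will see the patient at the start of HD1 Week 3 and HD1 Week 4". Session start times must be logged, the covariate model must be written into 8.2, and it should be confirmed that strips can be taken from the recording at chosen times. HD1 strips are not interchangeable with HD3 strips. The optional session means are noisier than the whole-period mean and add one more exploratory summary.

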The third relevant trial was the only study published to date that enrolled HD patients. In this study, six ESRD patients on HD were monitored for a 7-day baseline period, then they were administered patiromer 4.2g TID ²⁹. In this small study, the mean serum potassium decreased from 5.79 ± 0.31 mEq/L at baseline to 5.39 mEq/L during treatment, a mean decrease = 0.4 mEq/L (p=0.08). The mean fecal potassium excretion increased from 616 ± 203 mg/day during baseline to 975 ± 399 mg/day during treatment (P=0.02). The proportion of days with serum potassium < 5.5 mEq/L was 38% during the baseline period and 67% during the treatment period..

This current protocol includes an initial dose of patiromer of 8.4g once daily to be administered with the morning or mid-day meal. This will be titrated according to the pre-dialysis potassium values in weeks 1, 2 and 3 of the protocol.

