3.5 Adverse events with patiromer

In the published clinical trial of patiromer that was the longest duration (52 weeks), hypomagnesemia (7.2%) was the most common treatment-related adverse event, mild to moderate constipation (6.3%) was the most common gastrointestinal adverse event, and hypokalemia (<3.5 mEq/L) occurred in 5.6% of patients ²⁸.

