Randomization ¹			X													
Initiation of Patiromer ²				X												
Patiromer titration ³					X			X				X		X		
Physical Exam		X														
Vital Signs ⁴ (BP, HR, Height, Weight)		X			X				X			X		X		X
Renal Function Panel		X														
Serum Potassium			X	X	X				X			X	X	X	X	X
Serum Magnesium		X							X			X				X
Serum Pregnancy Test ⁵		X														
Holter Monitor Applied	X															X
Holter Monitor Removed			X													
Previous medication and concomitant medication		X	X	X	X				X			X		X	X	X
Adverse Event Questioning		X	X	X	X				X			X		X	X	X
Dialysis ⁶																
ECG	X	←								→						

1=Randomization can occur at any point after Week 0 HD1 as long as it is completed prior to Week 0, HD3.

2=If randomized to the Patiromer Arm

3=Patiromer will be increased by 8.4 g/day if K \geq 5.1 mEq/L, decreased by 8.4 g/day if K<4.0 mEq/L, and discontinued if K<3.5mEq/L

4= Blood Pressure taken after sitting for 5 minutes; Height only collected at Week 0, HD1

5=Females of child bearing potential

6= Hemodialysis should be performed 3 times per week

BIBLIOGRAPHY

6. System USRD. 2017 USRDS annual data report: Epidemiology of kidney disease in the United States. Bethesda, MD: National Institutes of Health, National Institute of Diabetes and Digestive and Kidney Diseases; 2017.

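### The Schedule of Assessments and Section 6 give two different patiromer titration and stopping rules

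*Combined protocol and SAP*

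**What the plan says.** Patients randomized to patiromer start on one 8.4 g packet a day, and the dose is adjusted on the HD1 potassium of Weeks 1, 2 and 3.

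Section 6.7 gives the increase rule as "Patiromer will be increased by 8.4 g/day if $K \geq 5.5$ meq/L" and the lower limits as "decreased by 8.4 g/day if $K < 4.5$ mEq/L, and patiromer will be discontinued if $K < 4$ mEq/L". Sections 6.13 and 6.14 repeat the same sentence.

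In Section 10, the titration row of the Schedule of Assessments points to footnote 3. There the increase rule is "Patiromer will be increased by 8.4 g/day if K \geq 5.1 mEq/L" and the lower limits are "decreased by 8.4 g/day if K<4.0 mEq/L, and discontinued if K<3.5mEq/L".

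The footnote is a complete sentence. Nothing restricts it to particular visits or patients or marks it as superseded, and the protocol has no statement of which part governs when two parts differ.

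**The concern.** The same drug, the same 8.4 g step and the same titration activity are governed by two sets of cut-offs. A coordinator working from the schedule on a visit day and one working from Section 6 could give different doses for the same potassium reading, and each would be following the protocol.

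The disagreement falls at two sensitive places. One is just under 5.5 mEq/L, the cut-off that defines an episode in the primary endpoint (Section 8.1). The other is the low end, where the question is when to reduce or stop a potassium-lowering drug in patients who also dialyse against 2 mEq/L potassium. Section 3.1 itself describes risk rising at low as well as high potassium.

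Monitoring is affected too. A significant protocol violation is grounds for withdrawal under Section 6.15, yet in the disputed bands a monitor could not say which dose was the violation.

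The point is the inconsistency. It takes no view on which thresholds are clinically better.

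**Working it through.** The protocol's only design calculation is the 86% power in Section 8.1. A two-sided two-sample t-test with 20 per group, difference 2, SD 2 and α = 0.05 gives 86.9%, so it reproduces. It plays no part in this point.

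**Step 1. Compare the rules across the potassium range.**

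| Pre-dialysis K (mEq/L) | Sections 6.7, 6.13, 6.14 | Footnote 3 | Agree? |
|---|---|---|---|
| < 3.5 | stop | stop | yes |
| 3.5 to < 4.0 | stop | decrease 8.4 g | no |
| 4.0 to < 4.5 | decrease 8.4 g | no change | no |
| 4.5 to < 5.1 | no change | no change | yes |
| 5.1 to < 5.5 | no change | increase 8.4 g | no |
| ≥ 5.5 | increase 8.4 g | increase 8.4 g | yes |

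**Step 2. Turn the actions into doses.** New dose = current dose + 8.4, unchanged, − 8.4, or 0 g/day. Entries are Section 6 versus footnote 3.

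| K band | From 8.4 g/day | From 16.8 g/day |
|---|---|---|
| 5.1 to < 5.5 | 8.4 vs 16.8 | 16.8 vs 25.2 |
| 4.0 to < 4.5 | 0 vs 8.4 | 8.4 vs 16.8 |
| 3.5 to < 4.0 | 0 vs 0 | 0 vs 8.4 |

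The footnote gives more drug in every cell but one. The exception is K 3.5 to < 4.0 on a single packet, where removing a packet and stopping are the same thing.

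**Step 3. How often might a reading fall in a disputed band?** This is illustration only. Assume HD1 potassium is normal with mean μ and standard deviation σ, so that

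P(a ≤ K < b) = Φ((b − μ)/σ) − Φ((a − μ)/σ).

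Section 3.4 reports from the six-patient hemodialysis study that "the mean serum potassium decreased from 5.79 ± 0.31 mEq/L at baseline to 5.39 mEq/L during treatment". I take μ = 5.79 and 5.39 from there and add μ = 5.0 as an assumption. For σ I use 0.31 (reading the ± figure as an SD, which the protocol does not state) and 0.5, 0.7 and 0.9 as assumptions. That study gave 4.2 g three times daily and its values are not specific to HD1.

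Worked example, μ = 5.39, σ = 0.31, band 5.1 to < 5.5: Φ(0.355) − Φ(−0.935) = 0.639 − 0.175 = 0.464.

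Each cell shows the bands 5.1–5.5 / 4.0–4.5 / 3.5–4.0 and then the total, in percent, rounded separately:

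| μ | σ = 0.31 | σ = 0.5 | σ = 0.7 | σ = 0.9 |
|---|---|---|---|---|
| 5.0 | 32 / 5 / 0; 37 | 26 / 14 / 2; 42 | 21 / 16 / 6; 43 | 17 / 16 / 9; 41 |
| 5.39 | 46 / 0 / 0; 47 | 31 / 3 / 0; 34 | 22 / 8 / 2; 32 | 18 / 10 / 4; 32 |
| 5.79 | 16 / 0 / 0; 16 | 20 / 0 / 0; 20 | 18 / 3 / 0; 21 | 15 / 5 / 2; 22 |

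Totals run from 16% to 47%. The 5.1 to < 5.5 band is the largest in all 12 combinations (15% to 46%). The 4.0 to < 4.5 band holds 0% to 16%, and the 3.5 to < 4.0 band 0% to 9%.

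**The case against.** The strongest reply is that the intended rule is easy to guess. It is stated three times in the operative section, Section 6.6 sends the reader there, and its 5.5 mEq/L trigger matches the endpoint cut-off and inclusion criterion 3. The schedule shows other signs of old text: it still refers to a Holter monitor where Section 6.10 specifies a patch worn for up to seven days. On that view this is a leftover footnote. The inference is reasonable and supports correcting the footnote rather than the body. But it remains an inference, and it does not help someone dosing from the schedule.

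A second reply is that the biggest disputed band is the mildest. From the starting dose, the dispute at 5.1 to < 5.5 is over one extra packet. The resulting 16.8 g/day is below the mean daily doses of 18.5 and 26.9 g reported in Section 3.4 for the 52-week non-dialysis trial. The stop-rule conflict covers few readings and changes the dose only at 16.8 g/day or more. This stands, and the 16% to 47% range must not be read as the size of the stopping problem.

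Two cautions on the inputs also stand:

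- The value below 3.5 is where a cited trial counted hypokalemia, in the words "hypokalemia (<3.5 mEq/L) occurred in 5.6% of patients" (Section 3.5). The protocol does not adopt it as its own definition.
- σ = 0.31 fits poorly as a spread of single readings. With μ = 5.79 it puts 17.5% of values below 5.5, while Section 3.4 reports 38% of baseline days below 5.5. Matching 38% needs σ of about 0.95, which gives a disputed total of about 23%.

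Neither caution touches the contradiction itself.

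**Conclusion.** The concern holds. The protocol contains two titration rules that differ in all three thresholds, so three potassium bands carry conflicting dose or stop orders. That follows from the wording alone and needs no assumption. In the disputed bands the dose differs by one packet (8.4 g/day) at the starting dose and at 16.8 g/day, apart from the one tie shown above. At higher doses the stop-rule gap is larger, because Section 6 stops the drug entirely and the footnote removes only one packet.

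The frequency range is a rough guide that depends on assumed means, spreads and normality. It shows only that disputed readings would be common rather than exceptional, chiefly between 5.1 and 5.5.

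This has to be corrected because the error sits in dosing and stopping instructions that staff act on. The conflict at the stopping end is confined to K 3.5 to < 4.0, since both rules stop below that.

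**What to change.** Change footnote 3 of the Schedule of Assessments to the Section 6 thresholds: increase at K ≥ 5.5, decrease at K < 4.5, discontinue at K < 4.0 mEq/L. Better still, have the footnote refer to Section 6.7 so that the rule is stated in one place.

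If the investigator and sponsor intended 5.1 / 4.0 / 3.5, change Sections 6.7, 6.13 and 6.14 instead. That would alter the dosing and stopping rule in three sections, so it should be handled as a dosing amendment rather than a clarification.

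For any patient already titrated, record which rule was applied at each adjustment.

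Correcting the footnote costs a short amendment or clarification memo. Neither route adds patients, visits or procedures.
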